129 **predispose toward an adverse profile of these mediators of pathophysiology.**

130 Substantial evidence suggests that euthymic individuals with histories of recurrent depression  
131 show greater rates of CVD, a pro-inflammatory state, impaired endothelial function, altered  
132 cardiac autonomic control, and elevated metabolic risk at levels equivalent to those seen in  
133 current depression. Based on this and evidence suggesting that histories of depression may  
134 predict the development of depression as well as functional impairment in the perimenopause,  
135 **we will employ historical recurrent depression as a model of vulnerability to depression.** In  
136 view of the shared physiologic perturbations seen in CVD and depression, perturbations that are  
137 likely to be amplified in the setting of estrogen deficiency, we predict that during the  
138 perimenopause, women with histories of depression will demonstrate greater likelihood of  
139 affective dysregulation (depression episodes, severity of depressive symptoms, functional  
140 impairment, and affective instability) and progression of cardiovascular risk.

141 Because stress **elicits a cascade of interrelated physiologic responses that negatively impact**  
142 **each of the “pathways” of risk described above,** exaggerated stress reactivity may play a  
143 pivotal role in the pathogenesis and comorbidity of depression and CVD. Cardiovascular  
144 reactivity to stress predicts cardiac events and the progression of atherosclerosis. Stress also  
145 activates proinflammatory cytokines in the periphery and CNS. Stress responses are also likely  
146 to play a role in metabolic risk., since glucocorticoids induce insulin resistance and individuals  
147 at metabolic risk show alterations in both sympathetic and hypothalamic-pituitary-adrenal  
148 (HPA)-axis activity. Thus, greater cardiovascular, inflammatory and HPA axis reactivities to  
149 stress (documented in both depression and in peri- and postmenopausal women), may comprise a  
150 phenotypic profile of risk that characterizes both depression and CVD. Further, a history of  
151 trauma exposure, which increases the risk for depression, metabolic disorders, and CVD and is  
152 associated with exaggerated sympathetic and HPA-axis reactivity. Thus, we predict that lifetime  
153 trauma exposure will explain some of the association between histories of depression and  

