561 history of sexual abuse; **2)** history of physical abuse; **3)** moderate or greater childhood physical  
562 neglect; **4)** moderate or greater childhood emotional neglect; **5)** presence of 7 other types of  
563 trauma (one point each) before the age of 18; **6)** presence of 4 lifetime traumas (1 point each).  
564 The measure of lifetime *sexual and physical abuse history* is based on previous studies by  
565 Investigator, [name], and adapted from other research. Cumulative trauma exposure has  
566 been shown to independently predict the development of adverse medical conditions, to be  
567 related to a variety of risk factors for the leading causes of death; and to predict CV reactivity to  
568 acute laboratory stressors.

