782 measures at months 0, 6, 12). Analyses which use outcomes measured repeatedly will use this  
783 repeated measures design for analysis, with mixed models for continuous outcomes and logistic  
784 models for categorical outcomes. The mixed models we will fit will be random coefficient  
785 models, which treat the time variable as numerical. We do this for several reasons: (1) it allows  
786 for a finer assessment of precisely when women come in for a “visit,” as visits rarely take place  
787 on exactly the day planned, and (2) the covariance structure is necessarily simpler, leading to  
788 more efficient mixed models. For comparisons assessing change over time, we will assess this  
789 change as a difference between treatments or groups, as stated with respect to specific  
790 hypotheses, on differences between baseline and month 12 least squares means (LSMs). The  
791 month 6 CV data will be part of the mixed model predicting the 12 month least squares means.  
792 That is, the mixed model is an Intent- to-Treat analysis which uses all available data to make a  
793 prediction about what outcomes we would see if all subjects had remained in through the 12  
794 month endpoint. Several outcomes are measured or derived only once over the follow-up period  
795 (e.g., presence of at least one depressive episode during follow-up, or affective instability during  
796 the follow-up period). For those outcomes, the model will not include a repeated factor, and will  
797 be a two-factor ANOVA or logistic regression. For each analysis, where appropriate, we will  
798 perform sensitivity analyses by adding potential mediators, moderators, or confounders (see

799 D.4.3.) in an appropriate way to the model to assess the effect of these confounders, and to better  
800 define mechanisms, and subjects for whom, for example, treatment is effective. Most  
801 hypotheses will be examined as main effects, interactions, or contrasts. Prior to statistical  
802 analyses, we will use descriptive statistics and graphics to screen the data for errors, outliers, and  
803 potential influential observations, and to check distributional assumptions. We will not blindly  
804 switch to non-parametrics if distributions within groups do not appear to be normal, but will  
805 judge whether the type and degree of non-normality are such which require rethinking our  
806 modeling assumptions. We have a relatively large sample size and our linear models should be  

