807 robust to relatively mild violations of normality. Even so, in the event we decide that the linear  
808 or linear mixed models we've selected are not appropriate, we will examine the possibility of  
809 testing hypotheses using permutation tests, sampling from the permutation distribution, in  
810 preference to non-parametrics.

811 We will define *affective instability* as the variance of each subject's CED-D total score over her  
812 follow-up period. We define the CV risk variable *Stress Reactivity*, as a composite formed in the  
813 following way: for IL-6, Mean Arterial Pressure, Vascular Resistance, and Cortisol, we will  
814 form the difference between resting and stress measures, yielding *reactivity* for each measure.  
815 We will calculate mean and SD for each measure at baseline (pre-treatment) and use those to  
816 standardize each measure at baseline (pre-treatment) and during the intervention to a common  
817 scale. We will then add the z-scores for the 4 measures together to form our stress reactivity  
818 composite at each point measured.

819 **Multiple Testing:** Several of the hypotheses use multiple outcome measures. We have in each  
820 identified one outcome as the primary outcome variable, and testing on this variable will be done  
821 without correction for multiple comparison. We will only examine other variables if the null  
822 hypothesis is rejected for the primary outcome variable. This enables us to follow significant  
823 effects with other analyses to explain or refine the response, helping us interpret the results.

824

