853 **affective well-being and CV risk.**

854 In the 320 women randomized to treatment we will test the following hypotheses:

855 **H1A:** Women on active treatment will show a decreased Stress Reactivity composite score over  
856 12 months relative to baseline levels and relative to the change (increased stress reactivity) in  
857 women on placebo. If confirmed, the following parallel hypotheses will be examined in  
858 hierarchical order: Women on active treatment will show 1) a lower rate of metabolic risk; and 2)  
859 increased endothelial flow-mediated dilatation and baroreceptor sensitivity. These hypotheses  
860 will be tested as main effects of treatment.

861 **H1B:** A history of DEP will predict a greater effect of ERT on Stress Reactivity: i.e., a greater  
862 decrease in Stress Reactivity (relative to baseline) between active and placebo treated women  
863 will be seen in women with a history of DEP (due to their higher baseline reactivity) compared  
864 with never DEP women. If confirmed, the following parallel hypotheses will be examined in  
865 hierarchical order: a history of DEP will predict a greater effect of ERT for 1) reductions in rate  
866 of metabolic risk, and 2) increased endothelial flow-mediated dilatation and baroreceptor  
867 sensitivity. These hypotheses will be tested as interactive effects (history by treatment).

868 **H2:** Although no subjects will be depressed at baseline, active treatment will be associated with  
869 a lower proportion of women experiencing episodes of DEP over 12 months relative to placebo  
870 treated women. If confirmed, the following parallel hypotheses will be examined in hierarchical  
871 order: Active treatment will be associated with: 1) lower CES-D DEP scores; 2) decreased  
872 functional impairment; and 3) decreased affective instability.

873 **H3: Secondary Hypothesis:** Treatment-related reductions in Stress Reactivity will partially  
874 mediate the beneficial effect of E2 on DEP episodes. If confirmed, the following parallel  
875 hypotheses will be examined in hierarchical order: Treatment reductions in Stress Reactivity will  
876 partially mediate reductions in 1) CES-D DEP rating scores; 2) Functional Impairment; and 3)  
877 Affective Instability (tested with sensitivity analyses).

878 **DATA ANALYTIC PLAN FOR EACH HYPOTHESIS**

879 **Aim 1 Hypothesis 1:** Since subjects have not yet been assigned to treatment, we will treat  

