906 parallel effects on metabolic risk (via a logistic regression), baroreceptor sensitivity, and flow  
907 mediated dilatation. Hypothesis H1B involves partitioning the interaction effect in these models.

908 **Aim 3 Hypothesis 2:** This will be examined in a logistic regression model with two between-  
909 subjects factors (DEP history and treatment) and the emergence of at least one DEP episode as  
910 the response. This is the treatment main effect in the model. If we reject the null hypothesis, we  
911 will examine the same hypothesis using CED-D total (mixed model), functional impairment  
912 (mixed model), number of episodes (Poisson regression), and affective instability (mixed model).

913 **Aim 3 Hypothesis 3 (secondary):** This hypothesis will use a logistic regression model with two  
914 between-subjects factors as above, the emergence of at least one DEP episode as the response,  
915 and stress reactivity in the model as a mediator.

916

917 **POWER AND SAMPLE SIZE CALCULATIONS FOR EACH SPECIFIC AIM:**

918 It is not feasible to conduct power analyses for every hypothesis. While this is a mechanistic  
 919 study designed, in part, to examine mediators of E2's beneficial effects on CV risk and DEP, we  
 920 must first be able to detect a beneficial effect of E2. Thus, we conduct power for Aim 3, H2.  
 921 We also felt it important, however, to confirm we are powered to detect meaningful differences  
 922 in the Stress Reactivity composite score since it is our primary CV outcome variable and also a  
 923 predicted mediator.

924 **Aim 3 Hypothesis 2:** Based on the work of Freeman et al (Menopause, 2009. **16**(4): p. 728-34)  
 925 for rates in untreated women, and our prediction that ERT will cut the rate of depression by 50%  
 926 (a clinically relevant difference), we predict the following percentages of women will experience  
 927 at least one DEP episode during the follow-up in our groups:

928

		Treatment Assigned	
		ERT	Placebo
Depression	Positive	22.5	45
History	Negative	15	30
(Combined)		(18.75%)	(37.5%)

929

930 The hypothesis corresponds to using logistic regression to test the depressive episode rate  
 931 between all those treated with ERT (18.75%) versus those treated with placebo (37.5%). Using a  
 932 logistic regression with this effect size, a two-tailed significance level of 0.05, and 240 total  
 933 subjects, power exceeds 96%. Further, power should be higher for the parallel poisson  

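### The Aim 3 H3 mediation model omits baseline Stress Reactivity and cumulative trauma, so stable differences between women bias the mediation estimate

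*Protocol*

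**What the plan says.** In the Protocol, Specific Aims and Hypotheses, Aim 3 H3 opens with "Treatment-related reductions in Stress Reactivity will partially" and goes on to mediation of estradiol's effect on episodes. Its subject is therefore a change within each woman that treatment brings about. The Data Analytic Plan for Aim 3 Hypothesis 3 gives the test: a logistic regression with two "between-subjects factors as above, the emergence of at least one DEP episode as the response", "and stress reactivity in the model as a mediator". The two factors are treatment and depression history. No visit is named for the mediator, and no baseline value or trauma score appears.

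General Statistical Considerations builds Stress Reactivity as a sum of four z-scores, a "composite at each point measured". That is a level at each visit, not a change.

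On trauma, Purpose and Rationale (item 4) refers to "trauma exposure, which increases the risk for depression, metabolic disorders, and CVD and is" linked with exaggerated sympathetic and HPA-axis reactivity. The Lifetime Trauma Exposure paragraph under Measurements says cumulative trauma has been shown "and to predict CV reactivity to" laboratory stressors. The trauma interview takes place at screening and the first stress test at Time 1, both before randomisation.

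General Statistical Considerations also says that, for each analysis and where appropriate, the investigators will "perform sensitivity analyses by adding potential mediators, moderators, or confounders (see" D.4.3. That section is not in the document at hand. The H3 paragraph ends "Affective Instability (tested with sensitivity analyses".

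**The concern.** Randomisation protects the path from treatment to reactivity. It does not protect the path from reactivity to episodes. Any lasting trait that raises both reactivity and liability to depression enters the reactivity coefficient, and the protocol itself names one such trait, trauma. A yes/no history term removes only the part of this that lies between the two history groups.

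If the mediator is the follow-up level, a woman who was reactive before treatment and prone to depression throughout contributes to the apparent reactivity-to-episode effect. When estradiol also lowers reactivity, as H1A predicts, the two paths together look like mediation even if the change in reactivity does nothing to mood. A positive H3 then opens three further mediation hypotheses: CES-D scores, functional impairment and affective instability.

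**Working it through.** **Plan's own figure.** H3 has none. The only figure for its response is the H2 power, stated as above 96% with 240 women. A two-sided two-proportion calculation (18.75% v 37.5%) gives 90.3% at 240 and 96.5% at 320. That is a separate matter and is not used below.

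**Set-up.** From the protocol: 320 women, 1:1 allocation, history strata, and the episode rates in the H2 table. Assumed, because the protocol gives no values:
- baseline-to-follow-up correlation r of 0.3 to 0.7
- odds ratio (OR) for an episode per SD of baseline reactivity of 1.5 or 2
- estradiol lowers reactivity by 0.4 SD
- follow-up reactivity has no effect of its own, so true mediation is zero

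Mediation is declared when the treatment-to-reactivity and reactivity-to-episode paths are both significant (|z| > 1.96).

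**What the omitted baseline does.** Let B be baseline and M follow-up reactivity, each with variance 1 within arm.
- Follow-up level: the slope of B on M is r, so M picks up a coefficient of about r × ln(OR).
- Change D = M − B: Cov(B, D) = r − 1 and Var(D) = 2 − 2r, so the slope of B on D is −1/2 and D picks up about −½ × ln(OR).

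With ln 1.5 = 0.405 and ln 2 = 0.693, the level gives 0.5 × 0.405 = 0.203 and 0.7 × 0.693 = 0.485. The change score gives −0.203 and −0.347. The simulated means are close to these.

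**Simulation, N = 320, 2,000 trials per row:**

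| r | OR | r × ln(OR) | Simulated coefficient (level) | False mediation, level | Level + baseline | Wrong-direction result, change score |
|---|---|---|---|---|---|---|
| 0.3 | 1.5 | 0.122 | 0.120 | 13.1% | 2.8% | 36.7% |
| 0.5 | 1.5 | 0.203 | 0.200 | 30.0% | 2.0% | 31.7% |
| 0.7 | 1.5 | 0.284 | 0.284 | 54.2% | 2.4% | 21.3% |
| 0.5 | 2 | 0.347 | 0.336 | 68.0% | 2.4% | 67.8% |
| 0.7 | 2 | 0.485 | 0.468 | 89.2% | 2.6% | 48.7% |

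The change score gave false protective mediation in 0% of trials in every row. At N = 240 (r = 0.5, OR 1.5) the level gave 22.7%, and 2.1% with baseline. The 2–3% is the nominal rate: power for the 0.4 SD path is 94.7% with 160 per arm, and 0.947 × 0.025 = 2.4%.

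**Adding trauma** (correlation 0.3 with baseline reactivity, OR 1.5 per SD, r = 0.5):
- Baseline reactivity (OR 1.5) and trauma both act: 72.6% as written, 10.6% with baseline only, 2.1% with both terms.
- Trauma alone acts: 18.2%, 9.7% and 2.7%. An unadjusted change score then gives 3.6% protective and 1.7% wrong-direction results.

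**If treatment does not move reactivity:** false protective mediation is 1.1% to 3.1% even without adjustment.

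**Other assumptions.** With r = 0.6 and baseline reactivity correlated 0.1, 0.2 or 0.3 with depression liability, the level model gave 9–11%, 25–32% and 43–65% (N = 240 to 320). At 0.2, adding baseline gave 2%. With trauma as the only shared cause, correlated 0.2, 0.3 or 0.4 with each, it gave 6–7%, 13–17% and 35–42%. At 0.4, baseline alone left 11–12%, and baseline plus trauma 2–3%. A further set with r of 0.5–0.6 gave 6–47% as written and about 2% with baseline. Its change-score results were 0–0.5% protective and 7–45% wrong-direction.

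**The case against.** The strongest reply is that the protocol already provides for confounders and that covariates for a secondary mediation analysis can be left to the SAP. The general clause covers every analysis and points to a list we cannot see, so one cannot say that trauma or baseline reactivity is absent from it. This stands as a limit on the claim. It does not repair the stated test: the clause makes such terms optional sensitivity analyses, and the protocol writes out the H3 model without them.

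A reader might infer that the plan will produce false mediation. The documents do not support that, for three reasons.
- Level or change is not fixed. The composite is defined as a level, but H3 speaks of reductions, and the power section approximates with change scores. Under an unadjusted change score the bias driven by baseline reactivity runs the other way.
- A spurious indirect effect requires treatment to move reactivity.
- The percentages rest on assumed correlations and on a joint-significance rule that the protocol does not state. At the weakest assumptions the excess is small.

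It is also tempting to cite Aim 1 H1, which expects higher baseline reactivity in women with past depression. History is already in the H3 model, so that hypothesis does not itself show residual confounding. The trauma statements carry the argument.

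Finally, H3 is labelled secondary. The randomised contrasts in H1A, H1B and H2 do not depend on it.

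**Conclusion.** The point holds in a conditional form. The H3 model as written does not condition on baseline Stress Reactivity or cumulative trauma, and the reactivity-to-episode path is not randomised, so the mediation estimate is open to bias from stable differences between women. For a follow-up level, with estradiol lowering reactivity, the bias is towards false mediation: about 6% to 89% of trials over the assumed range, against about 2–3% once the relevant baseline terms are included. For an unadjusted change score, bias from baseline reactivity tends to mask or reverse mediation. The direction follows from the algebra; the size cannot be fixed from the documents. It is worth correcting because H3 is the protocol's stated test of mechanism and the remedy costs almost nothing, but it touches a secondary hypothesis only.

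**What to change.** In the Data Analytic Plan for Aim 3 Hypothesis 3:
- Define the mediator as the follow-up Stress Reactivity composite at a named visit.
- Include the baseline composite and the cumulative trauma score as covariates in the episode model and in the matching treatment-to-reactivity model used for mediation.
- Report the present three-term model as unadjusted only.
- Use the same two covariates for the three parallel mediation hypotheses. Do not add baseline CES-D where month 0 is already a repeated response in the mixed model.

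Once baseline is in the model, level versus change no longer matters for the reactivity coefficient: b₁M + b₂B = b₁(M − B) + (b₁ + b₂)B, so b₁ is the same either way.

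The cost is a sentence or two of wording and two degrees of freedom, with no new data. The adjusted estimate still assumes no unmeasured shared causes of reactivity and episodes, which the report should say.

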## 302 **Study Design, Methods and Procedures**

303 **Overview of Protocol:** Briefly, medical and psychiatric evaluations will be conducted during an  
304 initial Screening period. Eligible women will then undergo initial Baseline Pretreatment  
305 assessments, including stress reactivity testing and assessments of baroreceptor sensitivity and  
306 endothelial function. Following Time 1 assessments, women will be randomized (in a 1:1  
307 fashion) to either transdermal 17 $\beta$ -estradiol (100 ug/day) or placebo for 12 months. Following  
308 randomization, during months 1, 2, 4, 6, 8, 10 and 12, compliance, side effects, vitals, depression  
309 symptoms and functional impairment will be assessed. Also, on a quarterly basis, oral  
310 micronized progesterone (200 mg/day x 12 days) will be given to ERT treated women. At the  
311 end of month 6 (Time 2 testing) and month 12 (Time 3 testing), while estradiol is still on board  
312 but prior to the final progesterone administration, all assessments conducted at baseline will be  
313 repeated. These events are described below.

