 934 regression on number of episodes, and for the analysis of the CES-D scores themselves.

935 **Aim 1, H1:** Our primary hypothesis for Aim 1 involves Stress Reactivity and since we cannot  
 936 assert that any stress-responsive factor is more important than another in this context, we will  
 937 combine different measures of stress-responsive CV risk factors and combine them into an index  
 938 called Stress Reactivity, described above. Since this measure has not been used before, we do  
 939 not have information from prior research on means and standard deviations which could help  
 940 with power and sample size calculations. Instead, we performed power calculations for each of  
 941 the stress reactivity variables which comprise the composite score. We used differences between  
 942 DEP and non-DEP groups from Pace et al. (Am J Psychiatry, 2006. **163**(9): p. 1630-3) for IL-6;  
 943 from Young et al. (Neuropsychopharmacology, 2000. **23**(4): p. 411-8) for cortisol; from  
 944 Brownley et al. (Am J Obstet Gynecol, 2004. **190**(4): p. 1052-8) for clinically relevant  
 945 differences in MAP; and from [name] (Health Psychol, 2007. **26**(2): p. 201-13; Int J  
 946 Psychophysiol, 1994. **17**(3): p. 233-48).for group differences in VRI – using the reported group  
 947 differences to define the magnitude of differences which are important, and to obtain estimates  
 948 of SDs. We obtained effect sizes of 0.63, 0.86, 1.0, and 1.5 for differences in delta MAP, VRI,  
 949 IL-6, and Cortisol, respectively. Our sample size of 160 per DEP group yields **99% power to**  
 950 **reject a null hypothesis** of no effect for an effect size of 0.63, (the smallest above), and 80%  
 951 power to detect an effect size as small as 0.40. Due to the complexity of the random coefficient

952 model to be used for this variable, we approximated our calculations with a simpler ANOVA  
953 power on change scores. Our actual power should be higher because the model should be more  
954 precise.

955 **Inducements for Participation**

956 Total possible monetary inducement for participating = \$1,275, prorated as follows:

957 \$100 for the medical and psychiatric screening (these screenings also provide benefit in the form  
958 of free medical evaluations)

959 \$150 for each laboratory test session (\$450 total)

960 \$100 for each flow mediated dilatation procedure (\$300 total)

961 \$ 25 for each interim study visit (\$125 total)

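### Two stated power figures do not match their sample sizes: 240 women give about 90% power for Aim 3 H2, not above 96%, and 160 per group detects about 0.31 SD at 80% power, not 0.40

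*Protocol*

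**What the plan says.** The section on power and sample size takes Aim 3 H2 as its main calculation. It compares the depressive-episode rate "between all those treated with ERT (18.75%) versus those treated with placebo (37.5%). Using a" logistic regression, and the next lines read "logistic regression with this effect size, a two-tailed significance level of 0.05, and 240 total" "subjects, power exceeds 96"%. The analysis plan for the same hypothesis says "This will be examined in a logistic regression model with two between"-subjects factors, namely DEP history and treatment. Allocation is equal: "Following Time 1 assessments, women will be randomized (in a 1:1" ratio).

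Elsewhere the randomised sample is 320. Aim 3 opens with "In the 320 women randomized to treatment we will test the following hypotheses". The Brief Summary and the Subjects section also give 320, and the randomisation section gives 160 per arm. I found 240 as a sample size only in the power statement, and the protocol gives no dropout rate or evaluable fraction.

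For Aim 1 H1 the same section says "Our sample size of 160 per DEP group yields 99% power to" reject the null at an effect size of 0.63, and 80% "power to detect an effect size as small as 0.40". No significance level is restated in that paragraph.

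**The concern.** Every input to the Aim 3 H2 calculation is printed, so the result can be checked without assumptions, and it does not reproduce. The protocol says that an effect of E2 must be detectable before mediators can be studied, and it picks this hypothesis to show that. Under its multiple-testing rule, CES-D scores, functional impairment and affective instability are examined only if this test rejects. If 240 really is the number analysed, the chance of missing the planned effect, and of closing that sequence with it, is about 10% rather than under 4%.

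The Aim 1 pair (160 per group, 80% power at 0.40) also fails to reproduce, in the other direction: it understates what the baseline comparison can detect.

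**Working it through.** **Aim 3 H2.** Inputs from the power section: p1 = 0.1875, p2 = 0.375, difference 0.1875, two-sided alpha 0.05, N = 240. With 1:1 allocation, n = 120 per arm. The mean rate is 0.28125.

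Pooled z-test:

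- SE0 = sqrt(2 × 0.28125 × 0.71875 / n)
- SE1 = sqrt((0.1875 × 0.8125 + 0.375 × 0.625) / n)
- power = Φ((0.1875 − 1.96 × SE0) / SE1)

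The stated figure was tried first, at the stated N:

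- n = 120: SE0 = 0.0580, SE1 = 0.0568, power = Φ(1.299) = **90.3%**. The stated figure is above 96%.
- n = 160: SE0 = 0.0503, SE1 = 0.0492, power = Φ(1.810) = **96.5%**.

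Other standard methods (two-sided 0.05; the adjusted models use the protocol's cell rates of 22.5, 45, 15 and 30%):

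| Method | 240 women | 320 women |
|---|---|---|
| Pooled z | 90.3% | 96.5% |
| Unpooled z | 91.0% | 96.8% |
| Exact power of the chi-square test | 90.6% | 96.6% |
| Logistic, adjusted for history, likelihood ratio | 90.7% | 96.6% |
| Logistic, adjusted for history, Wald | 89.3% | 95.9% |
| Log odds ratio, unadjusted Wald | 88.9% | 95.7% |
| Continuity-corrected | 87.5% | 95.4% |

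A one-sided 0.05 test at 240 gives only 93.8% to 95.1% depending on method, so a slip in sidedness does not explain the figure. By the pooled formula the smallest total for 96% is about 312 (156 per arm). At 240 the type II error is 100 − 90.3 = 9.7%, against less than 4% implied, a ratio of about 9.7 / 4 = 2.4.

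**Aim 1 H1.** Inputs: n = 160 per group, effect sizes 0.63 and 0.40. Two-sided alpha of 0.05 is assumed. Two-sample t-test, noncentrality d × sqrt(n/2), 318 degrees of freedom, critical value 1.967.

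- d = 0.63: noncentrality 0.63 × sqrt(80) = 5.63, power 99.99%. The stated 99% holds as a lower bound.
- d = 0.40: noncentrality 0.40 × sqrt(80) = 3.58, power **94.6%**. The stated figure is 80%.
- Effect at 80% power: normal approximation (1.960 + 0.842) × sqrt(2/160) = 0.313; exact t **0.314**.

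A stricter alpha does not recover 0.40: at 160 per group the effect detectable at 80% power is 0.375 for alpha 0.0125 and 0.384 for alpha 0.01. The stated pair, 99% at 0.63 and 80% at 0.40, fits about 99 per group (99.3% and 80.0%).

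**The case against.** The strongest defence is that the trial as planned has the power it claims. The protocol consistently randomises 320, and 320 gives 96.5%. On that reading one sentence carries a wrong N and nothing else is affected. Even at 240, power of about 90% is adequate by usual standards. The Aim 1 slip makes the trial look weaker than it is. All of this stands, and it limits the point to a correction of figures. It does not make the sentence right: an N of 240 and power above 96% cannot both hold for these rates.

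Four stronger readings are tempting, and the documents do not support them:

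- *The trial is underpowered.* A reader might take 240 as the evaluable number, since 240/320 = 75% would match 25% attrition. No such rate is printed, and the protocol does not call 240 the evaluable number.
- *The power and the N demonstrably come from two different calculations.* The match with 320 makes this plausible, but the protocol does not show how the figure was obtained.
- *All the stated power is wrong.* The 99% at 0.63 is a valid lower bound.
- *The remark about ANOVA on change scores is an error, because Aim 1 H1 is a baseline comparison.* General Statistical Considerations defines reactivity as the difference between resting and stress measures, and the power paragraph speaks of delta MAP. A change score can therefore exist at a single visit. The random-coefficient model named beside it belongs to Aims 2 and 3, where the same composite is analysed. The sentence is at most loosely placed, and it is the only statement of how that power was computed.

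**Conclusion.** Wrong as written, in two places.

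- **Aim 3 H2:** at the stated 240 women, power is about 90% (87.5% to 91% across two-sided methods), about six percentage points below the claim. The claim fits 320. This rests only on the printed rates, alpha and N, and on 1:1 allocation.
- **Aim 1 H1:** with 160 per group, power at 0.40 SD is about 95% and the effect detectable at 80% power is about 0.31 SD. This assumes two-sided 0.05 and a two-group comparison of means. The error is conservative.

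What remains open is which N the sponsor means for Aim 3 H2. If all 320 contribute outcome data, the planned power is about as stated. If 240 is the expected evaluable number, it is about 90%. The seriousness is that of a misstatement in the sample-size justification; neither the design nor the analysis is at fault on this point.

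**What to change.** Change the two power statements:

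- **Aim 3 H2:** *320 randomised, about 96% power; if 240 are evaluable, about 90%.* State which number the calculation refers to and, if 240 is an expected evaluable number, give the attrition assumption behind it.
- **Aim 1 H1:** *160 per group, two-sided 0.05: 80% power for 0.31 SD, about 95% for 0.40, above 99% for 0.63.*

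Keep the sentence on change scores. The cost is wording only: if 240 is meant, the Aim 3 figure becomes less favourable, while the Aim 1 figure becomes more favourable. Enrolment, endpoints, analyses and the testing sequence stay as they are.
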